## Plan for statistical analysis of efficacy and safety parameters

Table 3. Statistical analysis of the primary endpoint (template)

Total score on the "inattention" and "hyperactivity/impulsivity" subscales of the SNAP IV scale	Mexidol®				Placebo				Mexidol®+ Placebo			
	Visit 2 (Day 1)	Visit 5 (Day 43+1)	Dynamics		Visit 2 (Day 1)	Visit 5 (Day 43+1)	Dynamics		Visit 2 (Day 1)	Visit 5 (Day 43+1)	Dynamics	
			Abs.	%			Abs.	%			Abs.	%
N												
Mean												
95% CI, L												
95% CI, U												
Median												
Min												
Max												
Q 1												
Q 3												
Range												
Q Range												
SD												
CV												
Intragroup comparison: comparison of data at the end of therapy with data at the start of therapy (statistical criterion  ) (p-level value)												
Comparison of drugs (statistical test  ) (p-value)												
Indicator span diagram/ indicator scatter diagram												

 T-test for related samples or Wilcoxon test depending on the type of distribution of the indicator T-test for independent samples or Mann-Whitney test depending on the type of distribution of the indicator

Version 1.0 of 27.9.2019

Protocol-specific version for protocol #PHS-ADHD-002-MEX- TAB,  
version 3.0 dated 19.07.2019.

CONFIDENTIAL

page 32 of 42

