## 9. STATISTICS

### 9.1. *Description of statistical methods*

Demographic and other baseline patient characteristics (age, gender, disease duration, prior and concomitant disease, prior and concomitant therapy) will be compared between therapy groups to demonstrate comparability between groups at baseline using appropriate statistical tests.

Descriptive statistics for data whose distribution follows the law of normal distribution will be presented using the arithmetic mean and standard deviation. For otherwise distributed data descriptive statistics will be presented using non-parametric measures (median/mod, quartiles).

Two-sided confidence intervals will be used to assess treatment efficacy (primary and secondary efficacy criteria).

For primary and secondary efficacy criteria, differences will be considered statistically significant at the p-value level of <0.05.

In accordance with the purpose of the trial, statistical analysis of the results is planned to compare the efficacy of the therapy regimen including Mexidol® in the treatment of attention deficit hyperactivity disorder (ADHD) in children 6-12 years old at different dosing regimens with the efficacy of the regimen including placebo and a combination of the Investigational product and placebo.

The main efficacy criterion is the mean change in the total score on the inattention and hyperactivity/impulsivity subscales of the SNAP-IV scale after 6 weeks of therapy vs. baseline. Descriptive statistics for this indicator will be given and the following statistical hypotheses will be tested:

$$H^0: \mu_p = \mu_T; \\ H^1: \mu_T < \mu_p$$

$\mu_T$  - mean change in SNAP score in the trial group (group 1 Mexidol®, 125 mg OD, or group 2 (Mexidol®, 125 mg BID);

$\mu_p$  - mean change in SNAP score in control group 3 (placebo). The sign " $<$ " is associated with the fact that the change has a negative value.

Comparison of the values of the two groups of patients will be performed by calculating the two-sided 95% confidence interval for the difference of  $\mu_1$  ( $\mu_2$ ) and  $\mu_0$  values. A conclusion on superiority can be made if the upper bound of the two-sided 95% confidence interval for the difference in mean changes in SNAP scores of Mexidol® vs. placebo is negative.

Testing of the null statistical hypothesis can be done using one-factor analysis of variance with Dunnett's posterior criterion and evaluation of contrasts or similar applicable statistical analysis method.

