To assess the variability of the effect, the coefficient of variation (CV) value was calculated for all the above change values in the active treatment group:

$$CV = \frac{SD}{M}$$

The following values are obtained:

- 114%
- 167%

of which the maximum of 167% was used to estimate the standard deviation, which for the selected value of change corresponds to the value of  $4.5 * 1.67 = 7.515$ .

For the placebo group, the actual data above were used (-2.0 and -4.7 for mean and standard deviation, respectively).

In order to calculate the sample size, the following assumptions were made:

1. One-sided hypothesis of superior efficacy of Mexidol® over placebo.
2. The mean change in SNAP score in the placebo group is -2.0 points, and the standard deviation for the change is 4.70 points.
3. The mean change in SNAP score in the Mexidol® group is -4.5 points, and the standard deviation for the change is 7.515 points.
4. The modulus of the difference in mean SNAP scores between the Mexidol and placebo groups is 2.5 points
5. The pooled variance estimate (pooled variance) is:

$$SE = \sqrt{\frac{CO_1^2 + CO_2^2}{2}} = \sqrt{\frac{0.12, 0.46}{2}} = 6.27$$

6. The minimum adequate strength is 80% (consequently, the II error is 0.20).
7. The ratio of group volumes is 1:1:1:1.
8. The significance level is 95% (respectively, the I error is 0.05). Since the boundaries of the 95% confidence interval must be two-sided and testing of the superiority hypothesis is one-sided, a one-sided error I of 0.025 will be applied to test the hypothesis, which is equivalent to an error of 0.05 for a two-sided test.
9. 20% drop-out rate during screening.
10. 10% drop out rate during follow-up (based on the above studies).

All calculations were based on the formulae from the book (page 228), where the approximating function for power is given by the following equation

$$1 - \beta = 1 - F(t_{K,\alpha} - \Delta)$$

$$\frac{\sigma\sqrt{2/n}}{\Delta}$$

Where  $\Delta$  - clinically acceptable minimal difference (difference) from placebo and  $Fz = \int_{-\infty}^{z_{\alpha/2}} \text{Normal}(0,1) dz$ , which can also be written by the following expression for n:

$$n = \frac{2\sigma^2 [t_{\alpha/2} + z_{\beta}]^2}{\Delta^2}$$

Calculations were performed using the statistical package PASS 11 (NCSS Inc., USA), which is a validated package that uses formulae directly from the book by Chow et al. cited above.

The results of the calculations are as follows:

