## Plan for statistical analysis of efficacy and safety parameters

classification objectives). The protocol provides for the recording of all AEs that occur to the patient after the first administration of the trial therapy and until the end of the patient's participation in the trial. Frequency tables with data on discontinuation of therapy or changes in therapy parameters due to AEs will be presented. The choice of statistical criterion will be determined by the conformity/nonconformity to the normal distribution law and the dependence/independence of the samples being compared. Comparisons of safety performance between trial groups will be made using the  $\chi^2$ -square test (for qualitative data) and the t-test for data whose distribution follows the law of normal distribution, or its non-parametric analogue (for data whose distribution does not follow the law of normal distribution). The Mann-Whitney U-test will be used as the non-parametric analogue of the t-criterion.

Data obtained before the start and at the end of the trial will be compared to assess safety parameters.

To assess the robustness of the trial results, a sensitivity analysis will be performed on the main efficacy parameter: "Mean change in the total score on the inattention, hyperactivity/impulsivity subscale of the SNAP-IV scale after 6 weeks of therapy vs. baseline".

Since sensitivity analysis aims to assess the impact on the trial results of deviations from the methods of analysis used, as well as the impact of missing data values and a priori assumptions in order to identify the results that are most dependent on questionable or untenable assumptions, this trial includes an assessment of the impact of the following factors on the main conclusion of the trial:

- **Investigational site:** planned analysis adjusted for the covariate "Site" using a generalized linear model (GLM) to assess the consistency of the results with the analysis without introducing one;
- **Analysed populations:** in addition to the main analysis in the FAS population, a secondary analysis in the PP population is planned to assess the consistency of the results with the main analysis;

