**Plan for statistical analysis of efficacy and safety parameters**

with the efficacy of the regimen including placebo and a combination of the investigational product and placebo.

The main efficacy criterion is the mean change in the total score on the inattention and hyperactivity/impulsivity subscales of the SNAP-IV scale after 6 weeks of therapy vs. baseline. Descriptive statistics for this indicator will be given and the following statistical hypotheses will be tested:

$$H^0: \mu_p = \mu_T;$$
$$H^1: \mu_T < \mu_p$$

$\mu_T$  - mean change in SNAP-IV score in the experimental group (group 1 Mexidol®, 125 mg OD, or group 2 (Mexidol®, 125 mg BID);

$\mu_p$  - mean change in SNAP-IV score in control group 3 (placebo).

The sign " $<$ " is associated with the fact that the change has a negative value.

Comparison of the values of the two groups of patients will be performed by calculating the 95% confidence interval for the difference of  $\mu_1$  ( $\mu_2$ ) and  $\mu_0$  values. A conclusion on superiority can be made if the upper bound of the two-sided 95% confidence interval for the difference in mean changes in SNAP-IV scores of Mexidol® vs. placebo is negative.

Testing of the null statistical hypothesis can be done using one-factor analysis of variance with Dunnett's posterior criterion and evaluation of contrasts or similar applicable statistical analysis method.

The  $\chi^2$ -square test or Fisher's exact test will be used to assess differences in event rates.

The  $\chi^2$ -square test or Fisher's exact test will also be used to assess differences in patient adherence.

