## Plan for statistical analysis of efficacy and safety parameters

Table 6. Outcomes of the primary endpoint analysis

Total score on the "inattention" and "hyperactivity/impulsivity" subscales of the SNAP-IV scale	Inter-group differences			
	Mexidol® vs. Mexidol®+Placebo		Mexidol® vs. Placebo	
Statistical criterion				
p-level				
CI for difference in variances				
Superiority is proven (Yes/No)				

Table 7. Baseline anthropometric indices (template)

Indicator	Mexidol®				Placebo				Mexidol® + Placebo				General data			
	Age, years	Body weight, kg	Height, cm	BMI	Age, years	Body weight, kg	Height, cm	BMI	Age, years	Body weight, kg	Height, cm	BMI	Age, years	Body weight, kg	Height, cm	BMI
N																
Mean																
95% CI, L																
95% CI, U																
Median																
Min																
Max																
Q 1																
Q 3																
Range																
QRange																
SD																
CV																

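### The primary analysis is not fixed: SAP Table 6 lacks once-daily versus placebo, two different tests are named, and the planned 80% power fits only an unadjusted comparison

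*SAP*

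**What the plan says.** - **Decision rule.** SAP 6 and 7 and Protocol 9.1 use an interval for means: "A conclusion on superiority can be made if the upper bound of the two-sided 95% confidence interval for the difference in mean changes" is negative for Mexidol against placebo. SAP 6 and Protocol 9.1 also call primary differences significant at p below 0.05.
- **Test, in the text.** SAP 7 allows "one-factor analysis of variance with Dunnett's posterior criterion and evaluation of contrasts or similar applicable statistical analysis method". Protocol 9.1 is equally permissive: "Testing of the null statistical hypothesis can be done using one-factor analysis of variance with Dunnett's posterior criterion and evaluation of contrasts", again with a similar method allowed.
- **Test, in the shell.** Footnote 2 of SAP Table 3, the primary-endpoint table, says "T-test for independent samples or Mann-Whitney test depending on the type of distribution of the indicator".
- **Later changes.** SAP 6 and SAP 9 allow the list of methods to be altered once data collection is complete.
- **Comparisons.** The objectives and hypotheses (SAP 1 and 7, Protocol 3.2 and 9.1) are 125 mg once daily versus placebo and 125 mg twice daily versus placebo. SAP Table 6, which holds the yes/no superiority row, has columns for Mexidol versus Mexidol+Placebo and Mexidol versus Placebo. Its interval row reads "CI for difference in variances".
- **Sample size.** In Protocol 9.2, "The minimum adequate strength is 80" per cent and "a one-sided error I of 0.025 will be applied to test the hypothesis", which leads to 100 completers per arm.
- **Covariates.** The only one named is site, in a sensitivity analysis (SAP 6): "using a generalized linear model (GLM) to assess the consistency of the results with the analysis without introducing one".
- **Baseline.** Protocol 4.5.2 takes the screening SNAP-IV sum as baseline. Protocol 4.5.3 replaces it with the Visit 2 value when the visits are 7 or more days apart. SAP Tables 3 and 4 label every start column as Visit 2 (Day 1). Schedule 1.2 marks SNAP-IV at Visit 2 without the 7-day condition.

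**The concern.** A confirmatory trial with two dose-versus-placebo hypotheses needs one stated model, one interval and one table in which both hypotheses are decided. Here the text and the shell name different tests. The interval that decides superiority has no stated method or multiplicity status, and the methods may be revised after the data are in. The choice matters: power, familywise error, or both depend on it. The table that declares superiority cannot report one of the two primary objectives as drawn. Separately, a baseline score that every child has is not used to gain precision.

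**Working it through.** **Inputs (Protocol 9.2).** Difference 2.5; SD of change 4.70 (placebo) and 7.515 (Mexidol); 100 completers per arm; one-sided error 0.025. Three arms, 1:1:1.

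**1. The plan's own figure.**
Pairwise SD = sqrt((7.515² + 4.70²)/2) = 6.268 (stated as 6.27).
Standard error = 6.268 × sqrt(2/100) = 0.886, and 2.5/0.886 = 2.820.
Power = Φ(2.820 − 1.960) = 80.5% (80.1% by noncentral t). The t-based requirement is 100 per arm, so the stated size reproduces. It matches an unadjusted two-group comparison.

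**2. The same size under Dunnett.** For two contrasts with correlation 0.5 and 297 df, the two-sided critical value is 2.223 (numerical integration).
- Pairwise SD: Φ(2.820 − 2.223) = 72.5%. For 80%: 2 × 6.268² × (2.223 + 0.842)²/2.5² = 118.04, so 119 per arm.
- If both doses have SD 7.515 and the ANOVA pools all three arms: error SD = sqrt((2 × 7.515² + 4.70²)/3) = 6.709. Power = Φ((2.5/sqrt(0.02) − 2.223 × 6.709)/6.268) = 67.0%. For 80%: 2 × (2.223 × 6.709 + 0.842 × 6.268)²/2.5² = 130.4, so 131 per arm.

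**3. The same size without adjustment.** Two two-sided 0.05 tests share the placebo arm. Familywise error = 1 − P(both statistics within their limits), with correlation 0.5 and 297 df, = 9.1%. It is 4.5% in the favourable direction. Dunnett holds these at 5% and 2.5%.

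**4. Baseline adjustment.** The gain depends on R², the share of within-arm change variance that baseline explains. The documents do not give it, so the values below are assumptions. Unadjusted-limit power = Φ(2.820/sqrt(1 − R²) − 1.960).

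| Assumed R² | 0% | 10% | 20% | 35% |
|---|---|---|---|---|
| Power | 80.5% | 84% | 88% | 94% |

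Under Dunnett with the pairwise SD, 80% at 100 per arm needs R² = 1 − (2.820/(2.223 + 0.842))² ≈ 15%. With the three-arm SD it needs about 26% of the pairwise change variance.

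**5. Test against interval.** A Mann-Whitney p-value is not a test of the difference in means. The plan itself assumes unequal SDs (4.70 and 7.515), so the p-value and the interval for means need not agree. With both p below 0.05 and the interval rule stated, the plan does not say what happens if they differ.

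**6. Table 6 against the hypotheses.** Under Protocol 6.1, group 1 (once daily) takes Mexidol plus placebo, and group 2 (twice daily) takes Mexidol only.

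| Comparison | Primary hypothesis | Table 6 column |
|---|---|---|
| Once daily vs placebo | Yes | No |
| Twice daily vs placebo | Yes | Yes |
| Twice daily vs once daily | No | Yes |

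**7. Baseline labels.** A child whose visits are less than 7 days apart need not have a Visit 2 SNAP-IV rating under Protocol 4.5.3. The Visit 2 label therefore conflicts with the baseline rule in Table 3 and in the inattention and hyperactivity/impulsivity rows of Table 4. Visit 2 is the right start for SCAS, ADHD Rating Scale-IV and PedMIDAS. The protocol gives no baseline-value rule for CGI-ADHD-S, the oppositional defiant subscale or the Conners index.

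**The case against.** Several points on the other side have force.

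- **Baseline adjustment is a preference.** A reader might infer that the unadjusted comparison of changes is biased. It is not: under randomisation it is valid, and the gain from ANCOVA may be nil. This stands, so baseline is an improvement and not an error.
- **The once-daily comparison is planned.** A reader might infer from Table 6 that it was dropped. SAP 7 states the hypothesis, and Table 3 has columns for both arms and a comparison row. The gap is confined to Table 6. Its source may be the loose sentence in SAP 7 and Protocol 9.1 about comparing with placebo and with a Mexidol-placebo combination. The variances wording is probably a slip, since every statement of the rule concerns means. The missing column remains.
- **A rank test cannot decide superiority, because the interval rule does.** This holds only in part: p below 0.05 also applies to the primary criterion, and Table 6 has a p-value row beside the superiority row.
- **The Dunnett power loss is a multiplicity question.** It is, but Dunnett is the procedure both documents name, so its consequence belongs here. The 67% figure needs an added assumption: Protocol 9.2 gives a single Mexidol SD and pools it pairwise.
- **The baseline label may be a version difference.** The SAP cites protocol 3.0 and the protocol supplied is 4.0. SAP 3 plans no departure from the protocol, so the documents do not show that a wrong baseline would be used. This is a labelling conflict.

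**Conclusion.** The concern holds as a specification fault that should be corrected before lock; the documents do not show an invalid trial. In order of weight:

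1. Table 6 cannot report the first primary objective and names the wrong quantity for its interval.
2. Two different primary tests are named, the status of the deciding interval is open, and methods may change after data collection.
3. The sample size supports 80.5% power only with unadjusted limits, at about 9.1% two-sided familywise error. Under Dunnett, per-dose power is 72.5%, or about 67% with the three-arm SD.
4. Precision available from baseline SNAP-IV is unused, by an unknown amount.
5. The SNAP-IV start column needs relabelling.

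A reader might conclude that the trial is underpowered. That follows only if Dunnett limits are used and baseline explains less than about 15% (pairwise SD) to 26% (three-arm SD) of the change variance; the documents settle neither. The power figures rest on the plan's own difference and SDs, and every R² is assumed.

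**What to change.** In the SAP, before database lock and unblinding:

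- Name one primary model: ANCOVA of the change in the SNAP-IV inattention plus hyperactivity/impulsivity sum on arm and baseline sum. Take the Dunnett-adjusted estimate, interval and p-value for each dose versus placebo from it.
- Restate per-dose power at 100 per arm, before baseline adjustment, as about 67–72.5%.
- Replace Table 3 footnote 2 for the primary endpoint. Keep the rank-based and site-adjusted analyses as sensitivity analyses.
- Exempt the primary analysis from the clauses in SAP 6 and 9 that allow methods to change after data collection, and remove the similar-method option.
- Redraw Table 6 with once daily versus placebo and twice daily versus placebo, and the interval for the difference in mean changes. Align the combination sentence in SAP 7 and Protocol 9.1.
- Label the start column Baseline, under the Protocol 4.5.2–4.5.3 rule, in Table 3 and in the two affected SNAP-IV rows of Table 4. State separately which visit is baseline for CGI-ADHD-S, the oppositional defiant subscale and the Conners index. Reconcile schedule 1.2 with Protocol 4.5.3.

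Cost: SAP text and table shells, one degree of freedom for a covariate whose gain may be nil, and a less favourable stated power. No new data are needed at the present size; holding 80% under Dunnett without help from baseline would take 119 to 131 completers per arm. Any wording change in Protocol 9.1 or schedule 1.2 goes through the amendment process in Protocol 11.2.

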## Plan for statistical analysis of efficacy and safety parameters

Table 4. Statistical analysis of secondary, endpoints (SNAP-GU, CGI-ADHD-S, SCAS, PedMIDAS and ADHD Rating Scale IV) (template)

Indicator 	Mexidol®				Placebo				Mexidol®+ Placebo			
	Visit 2 (Day 1)	Visit 5 (Day 43+1)	Dynamics		Visit 2 (Day 1)	Visit 5 (Day 43+1)	Dynamics		Visit 2 (Day 1)	Visit 5 (Day 43+1)	Dynamics	
			Abs.	%			Abs.	%			Abs.	%
N												
Mean												
95% CI, L												
95% CI, U												
Median												
Min												
Max												
Q 1												
Q 3												
Range												
QRange												
SD												
CV												
Intragroup comparison: comparison of data at the end of therapy with data at the start of therapy (statistical criterion  ) (p-level value)												
Comparison of drugs (statistical test  ) (p-value)												
Indicator span diagram/ indicator scatter diagram												

 - SNAP-IV subscale score - "inattention."

- SNAP-IV subscale score - "hyperactivity/impulsivity."

- SNAP-IV subscale score - oppositional defiant disorder;

- SNAP-IV subscale score - Conners index;

Clinical Global Impressions-ADHD-Severity scale (CGI-ADHD-S).

- Spence children's anxiety scale (SCAS) scores after 6 weeks of therapy compared to baseline;

PedMIDAS questionnaire score

- ADHD Rating Scale-IV score after 6 weeks of therapy compared with baseline.

 T-test for related samples or Wilcoxon test depending on the type of distribution of the indicator T-test for independent samples or Mann-Whitney test depending on the type of distribution of the indicator**Version 1.0 of 27.9.2019**Protocol-specific version for protocol #PHS-ADHD-002-MEX- TAB,  
version 3.0 dated 19.07.2019.**CONFIDENTIAL**

page 33 of 42

## Plan for statistical analysis of efficacy and safety parameters

Table 5. Statistical analysis of secondary endpoints (CGI-I scale) (template)

The Clinical Global Impressions Scale - Improvement (CGI-I) score.	Investigational products		
	Mexitol®	Placebo	Mexitol®+ Placebo
N			
Mean			
95% CI, L			
95% CI, U			
Median			
Min			
Max			
Q 1			
Q 3			
Range			
Q Range			
SD			
CV			
Comparison of drugs (statistical test  ) (p-value)			
Indicator span diagram/ indicator scatter diagram			

 T-test for independent samples or Mann-Whitney test depending on the type of distribution of the indicator

## Plan for statistical analysis of efficacy and safety parameters

Table 6. Outcomes of the primary endpoint analysis

Total score on the "inattention" and "hyperactivity/impulsivity" subscales of the SNAP-IV scale	Inter-group differences			
	Mexidol® vs. Mexidol®+Placebo		Mexidol® vs. Placebo	
Statistical criterion				
p-level				
CI for difference in variances				
Superiority is proven (Yes/No)				

Table 7. Baseline anthropometric indices (template)

Indicator	Mexidol®				Placebo				Mexidol® + Placebo				General data			
	Age, years	Body weight, kg	Height, cm	BMI	Age, years	Body weight, kg	Height, cm	BMI	Age, years	Body weight, kg	Height, cm	BMI	Age, years	Body weight, kg	Height, cm	BMI
N																
Mean																
95% CI, L																
95% CI, U																
Median																
Min																
Max																
Q 1																
Q 3																
Range																
QRange																
SD																
CV																

